Post Medical Visit Provider and Veteran Interviews: Providers and veterans who agree will be interviewed briefly by phone about their experience during the medical visit with a focus on CC. Willing veterans will be interviewed regardless of whether their provider does an interview. We will plan to conduct these interviews within one week of the scheduled appointment. If the non-VA provider agrees to complete a qualitative interview, a separate consent letter will be provided at that time prior to data collection detailing the information to be obtained. Again, a waiver of signature of consent will be utilized with clear instructions that by completing the audio recorded interview that he/she is providing consent to participate. The interview will address two main issues: the impact of the information exchange on the visit, and the acceptability and optimal design of a co-management care coordination agreement.

Outcome Assessments and Quantitative Analysis: The main outcomes of this study and when they will be collected are presented in Table 2. Though ordered in the table, we will not dictate what order the VA and non-VA provider appointments must occur – though this order will be noted in data collection. As this is a pilot study, we are conducting analyses to determine an estimate of effect size and expected variability to be used in a later power calculation for a larger experimental or quasi-experimental study.

Table 2: Study Assessments

Outcome			
Patient Perceptions of Integrated Care	Baseline	Post VA Visit	Post Non-VA Visit
Provider Relational Coordination Survey		Post VA Visit	Post Non-VA Visit
Medication Concordance- From Chart		Post VA Visit	Non-VA Visit
Medical Duplication- From Chart		Post VA Visit	Post Non-VA Visit

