Hypothesis 1: Patients in the intervention arm will have greater increase in the Perceptions of Integrated Care Survey score from baseline to the two provider visits when compared with usual care. This hypothesis will involve three dependent sample t-tests, assuming that Patient Perceptions of Integrated Care are distributed normally (if not normally distributed, analyses will use a Wilcoxon rank sum test). Specifically, we will examine differences between intervention and usual care patients with respect to the within-patient change between baseline perceptions and 1) perceptions after the first subsequent visit with a VA provider, 2) perceptions after the first subsequent visit with a non-VA provider, and 3) perceptions after subsequent VA and

non-VA provider visits averaged. Sub-analyses looking for differences between demographic groups based on age and gender will also be conducted.

Hypothesis 2: Providers in the interventional arm will have higher scores on the Relational Coordination Survey as compared to that of providers in usual care. The Relational Coordination survey will be completed by providers at each patient's first VA visit and first non-VA visit subsequent to baseline. Assuming coordination perceptions are normally distributed, analysis will use independent sample t-tests to evaluate differences in relational coordination perceptions between providers caring for patients in the treatment and usual care groups (alternatively, the Wilcoxon test may be used for non-normal measures). Differences in perceptions between usual care and treatment groups will be evaluated separately for VA providers and non-VA providers. These analyses assume that no two patient participants share a provider. If this assumption is not met, analyses will be adjusted to account for clustering within physician.

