Hypothesis 3: Medication concordance will be higher for patients in the intervention arm than usual care. Medication concordance for each of the two medical visits will be calculated by making two lists, the current VA medication list and the current non-VA medication list. The former will be taken from CPRS while the latter will be taken from the non-VA provider visit most proximal temporally to the VA visit. We will obtain both the visit note and the medication list from the providers' visits. If the note does not indicate any medication change and there is none indicated on the form we ask the provider to complete, the provider's medication list will be designated the final medication list documented for that visit. If there is an indication of a specific medication change, either in the note, or in the form we request providers to complete, the discrepancy pertaining to this change will not be counted as an "unreconciled" medication.

Our metric for concordance of medication lists will be based on reviewing both the VA and non-VA medication lists and determining the total number of distinct medications. A distinct medication is defined by 1) the type of medication and 2) the daily dose. The final calculation of appropriate medication concordance will be calculated as the total number of distinct medications included on both lists divided by the total number of distinct medications. This way, the possible range is from 0 to 1 with 1 indicating perfect concordance of medication lists. The metric will range from 0 to 1, but we expect agreement between the two medication lists to yield estimates ranging between 0.50 and 0.90 based on prior research in medication appropriateness(10, 21). We will first examine the distribution of medication concordance to determine the appropriate statistical test. If the distribution is highly skewed, we may categorize the variable into two or more categories (e.g., <10%, 50%, or >=80% agreement) and evaluate differences between patients in the intervention and usual care groups using a Chi-square test. Alternatively, medication concordance may be treated as a continuous variable and evaluated using the t-test or Wilcoxon rank sum.

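### Hypothesis 3 permits a highly skewed concordance score to be cut at unfixed points and tested by chi-square, although the Wilcoxon test it also lists handles skew and keeps the ordering of scores

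*Combined protocol and SAP*

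**What the plan says.** Hypothesis 3 in the combined protocol and SAP defines concordance for each of the two visits as "the total number of distinct medications included on both lists divided by the total number of distinct medications", so each patient has a score between 0 and 1. On its likely values the plan says "we expect agreement between the two medication lists to yield estimates ranging between 0.50 and 0.90".

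The test is not fixed in advance: "We will first examine the distribution of medication concordance to determine the appropriate statistical test". For strongly skewed scores the plan allows grouping, in these words: "we may categorize the variable into two or more categories (e.g., <10%, 50%, or >=80% agreement"). The arms would then be compared by chi-square. The next sentence gives another route: "medication concordance may be treated as a continuous variable and evaluated using the t-test or Wilcoxon rank sum". The section does not say how much skew counts as high, which route then applies, or what the final cut points are.

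Hypotheses 1 and 2 meet non-normal data without any cutting. The first says "if not normally distributed, analyses will use a Wilcoxon rank sum test" and the second says "alternatively, the Wilcoxon test may be used for non-normal measures".

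The section on outcome assessments and quantitative analysis gives the purpose of all these analyses: "we are conducting analyses to determine an estimate of effect size and expected variability to be used in a later power calculation". It does not name the scale on which effect size is to be expressed.

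**The concern.** Skew is a reason to avoid relying on normality. It is not a reason to group the data. The rank sum test does not need normality and uses the full ordering of the scores. A two-way cut keeps only which side of the line a patient falls on. Pearson's chi-square on three or more categories also ignores their order, although the hypothesis is directional.

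The example cuts fit the plan's own expectation poorly. If patient scores lie between 0.50 and 0.90, nobody falls below 0.10 and only the 0.80 line separates patients. The three example labels also leave gaps in the scale.

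Two things are at stake. The first is power in a sample of 60. The second is that the cuts are open: nothing requires them to be set before the arms are compared, and a cut chosen after looking would not keep the nominal error rate.

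**Working it through.** The plan states no alpha, power, effect or SD for this outcome, so there is no figure of its own to reproduce. The size has to come from simulation.

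**Inputs from the plan:** 60 patients in two arms; score = matched drugs / distinct drugs; expected range 0.50 to 0.90; example cuts 0.10, 0.50 and 0.80.

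**Assumptions:** 30 per arm; two-sided 5%; the number of distinct drugs N per patient uniform on 4–8, 5–12 or 8–15; true agreement p per patient as below; score = Binomial(N, p)/N. Wilcoxon uses the tie-corrected normal approximation. Chi-square is uncorrected, with empty categories dropped. Power is the share of 10,000 simulated trials with p-value below 0.05, so its Monte Carlo standard error is at most √(0.5 × 0.5 / 10,000) = 0.5 points.

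- *Case A, strongly skewed toward 1:* p is Beta with mean 0.80 vs 0.88 and SD 0.15. With k = m(1 − m)/SD² − 1, k = 0.16/0.0225 − 1 = 6.11 and 0.1056/0.0225 − 1 = 3.69, and the parameters are mk and (1 − m)k. Pooled skewness is about −1.25.
- *Case B, true agreement inside 0.50–0.90:* p = 0.5 + 0.4 × Beta(2.77, 0.92) vs 0.5 + 0.4 × Beta(1.52, 0.22), with means 0.80 vs 0.85.

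| Case | Drugs | Wilcoxon | Chi-square at 0.80 | Loss (points) | Chi-square at 1.0 |
|---|---|---|---|---|---|
| A | 4–8 | 42.3% | 28.4% | 13.9 | 43.9% |
| A | 5–12 | 48.8% | 28.6% | 20.2 | 50.0% |
| A | 8–15 | 55.2% | 31.8% | 23.4 | 55.7% |
| B | 4–8 | 20.2% | 15.8% | 4.4 | 15.0% |
| B | 5–12 | 24.5% | 19.1% | 5.4 | 14.5% |
| B | 8–15 | 30.1% | 23.5% | 6.6 | 14.7% |

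Across repeat runs the losses at 0.80 were about 13 to 23 points in case A and 3 to 7 in case B. Using all three example cuts in case A lowers power further, to 20.3%, 21.0% and 24.1%.

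**Rounded scores.** If the score is round(pN)/N instead, the loss at 0.80 is 27 to 36 points in case A (for example 69.0% − 33.4% = 35.6) and 3 to 32 in case B (46.8% − 43.8% = 3.0; 80.3% − 48.6% = 31.7). Rounding removes the sampling variation in the number of matched drugs, so I do not rest the point on these figures.

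**Different assumptions.** In nine beta-binomial scenarios (6 to 14 drugs, arm means 0.65 vs 0.80, 0.70 vs 0.85 and 0.75 vs 0.90, 4,000 trials each), the loss was 11 to 18 points at 0.80 and 20 to 34 with all three cuts. With cuts at 0.50 and 0.80, 23% to 98% of trials had an expected count below 5.

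**The lowest category.** At most 1.2% of scores fell below 0.10, which is 0.012 × 60 = 0.7 patients.

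**Type I error.** With the cut fixed at 0.80 and the test chosen from pooled skewness, the error rate is 4.6% to 5.3%. If instead the best of five cuts (0.5, 0.6, 0.7, 0.8, 0.9) is taken after the arms are compared, it is about 15% to 17% (beta-binomial scores, mean 0.75 in both arms).

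**Effect estimate under ties.** In case A with 4–8 drugs, the Hodges-Lehmann difference was exactly 0 in about 55% of trials and averaged just under 0.05, against a true mean difference of 0.08.

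**The case against.** The plan only permits categorising. It gives its cuts as examples and offers Wilcoxon in the next sentence, so nobody is bound to the weaker test. A reader might infer that the plan commits to chi-square on these three categories; the text does not say so.

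This is also a pilot aimed at effect size and variability, so power is secondary. Cutting for one test does not destroy the raw scores, and nothing prevents the team from reporting a mean and SD. That stands. It limits the weight of the point but does not remove it: the option serves no purpose that the listed Wilcoxon test does not serve, and the Hypothesis 3 test remains undefined while both are open.

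The size depends on assumptions. With agreement inside the plan's expected range and binomial counts, the loss is only a few points on power of 20% to 30%. When scores pile up at 1, a cut at 1.0, which the open wording allows, beats Wilcoxon by 0.5 to 1.6 points with counts and about 6 to 7 with rounded scores. Both are conceded. The plan does not name that cut, and in case B it gives only about 15%.

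Finally, naming Wilcoxon also removes the t-test option, which is not itself at fault. That is a cost of settling on one test, and it is small.

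**Conclusion.** The point holds as a moderate one. Skew alone does not justify categorising this score, and the plan already lists a test that deals with skew. At the plan's 0.80 cut, chi-square had less power than Wilcoxon in every scenario simulated: about 3 to 7 points less with counts and agreement within 0.50 to 0.90, and about 13 to 23 less with strong skew toward 1. These figures assume 30 per arm and the stated list sizes, distributions and effects, none of which the plan gives. They show direction and rough size.

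Two stronger readings are not supported. One is that inspecting the distribution first invalidates the test: choosing from pooled skewness with a fixed cut leaves the error rate near 5%. The other is that the plan intends to pick cuts after seeing the arms. It states no such intent; the 15% to 17% error rate is a risk left open by unfixed cuts. Equally, the issue cannot be called one of power alone while that risk remains.

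**What to change.** - Delete categorisation with chi-square as a test of Hypothesis 3. State in advance that the uncut score is compared between arms at each visit by the tie-corrected Wilcoxon rank sum test.
- Report the mean difference with a 95% CI (for example by bootstrap) and the SD as the inputs to the later power calculation. Do not make the Hodges-Lehmann difference the headline estimate, because heavy ties can set it to exactly 0.
- Show the proportions with at least 80% agreement and with perfect concordance by arm, descriptively, with those cuts fixed in advance.

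Only analysis wording changes. The cost is about 2 points of power against the t-test if the data are normal (78% vs 80% in simulation), and about 1 to 7 points against a cut at 1.0 if scores pile up at 1.

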Hypothesis 4: Medical duplication will be lower for patients in the intervention arm than usual care. Prior research has quantified therapeutic and laboratory duplication, yet these are clearly difficult constructs to operationalize(10, 21-23). Therapeutic duplication will be defined as concurrent use of more than one medication from the same therapeutic class, based on modified VA classes, according to the method published by Fitzgerald et al. (24) and more recently adapted by Chrischilles et al.(10). For laboratory duplication, we will identify all orders for labs occurring within the 6 months prior to the non-VA provider visit. For sensitivity analysis, we will compare different intervals, e.g., 14 days, 30 days, 60 days. Since there are multiple indications for laboratory referrals, we will collect temporally associated diagnoses. Each patient will be assigned a dichotomous indicator for whether they received therapeutic duplication and/or laboratory duplication during their non-VA provider visit.

To validate these metrics, all instances of identified duplication plus a random sample of visits where no apparent duplication occurred will be reviewed by [name], a clinical pharmacist, and [name], head of the ICVAHCS pathology department. Both are current collaborators on [name] HSR&D and ORH study. Drs. [name] and [name] will be blind to whether or not the visit met criteria for treatment or diagnostic redundancy and they will also be blind to the treatment arm of the patient whose visit is being reviewed. Their clinical assessment of presence of duplication will be used to validate the metric. If agreement is poor between these two raters and the criteria described above (Kappa > 0.80), the investigative team will meet to determine the source of the discrepancy and how to remedy it. Each patient will be assigned a dichotomous indicator for whether they received either therapeutic or laboratory duplication during their non-VA provider visit. Differences in the occurrence of medical duplication between usual care and intervention groups will be examined using the Chi-square test.

REFERENCES

1. 2011 Survey of Veteran Enrollees' Health and Reliance upon VA. . 2011.

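### The validation rule for the duplication metric gives Kappa > 0.80 as its number for poor agreement; read literally, it calls for a remedy at kappa 0.95 and not at 0.30

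*Combined protocol and SAP*

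**What the plan says.** The passage is in the combined protocol and SAP, under Hypothesis 4, where the plan describes how the therapeutic and laboratory duplication measures will be validated. A clinical pharmacist and the head of pathology review every visit flagged as a duplication plus a random sample of unflagged visits. They are blind to study arm and to whether the visit met the criteria. The role of this review is stated plainly: "Their clinical assessment of presence of duplication will be used to validate the metric".

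The decision rule follows: "If agreement is poor between these two raters and the criteria described above (Kappa > 0.80), the investigative team will meet". The purpose of that meeting is given in the rest of the sentence: "the investigative team will meet to determine the source of the discrepancy and how to remedy it".

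The measure then becomes the outcome: "Each patient will be assigned a dichotomous indicator for whether they received either therapeutic or laboratory duplication during their non-VA provider visit". It is compared between arms: "Differences in the occurrence of medical duplication between usual care and intervention groups will be examined using the Chi-square test".

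**The concern.** The parenthesis is attached to a condition about poor agreement, but the number in it describes high agreement. It also conflicts with the action it triggers, since a meeting to trace and remedy disagreement has least to do when kappa is highest.

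The plan itself acknowledges that duplication is hard to define, and the blinded review is its safeguard. The kappa rule is the only numerical trigger for revising the measure. Followed as printed, it would let a poorly agreeing measure pass unremedied into the Chi-square comparison and would call a meeting over a sound one. Under Outcome Assessments and Quantitative Analysis the pilot's stated purpose is that "we are conducting analyses to determine an estimate of effect size and expected variability to be used in a later power calculation". A misclassified duplication indicator would carry over into those estimates for this outcome.

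**Working it through.** **Inputs from the plan.** The threshold is Kappa > 0.80, the condition is poor agreement, and the action is a meeting to find and remedy the discrepancy (all Hypothesis 4). The plan gives no number of visits to be reviewed, so the counts below are assumptions for illustration. There is no sample size, power or alpha figure to reproduce for this point.

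**Step 1: direction of the scale.** Cohen's kappa = (po − pe)/(1 − pe), where po is observed agreement and pe is chance agreement. With po = 1, kappa = 1; with po = pe, kappa = 0. So kappa rises with agreement. At kappa = 1 there is no disagreement at all, yet 1 > 0.80 and the printed rule fires. At 0.95 it fires; at 0.30 it does not. This step needs no assumption.

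**Step 2: illustration in counts.** Take one reviewer's assessment against the criteria, with D disagreements.

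*Assume 20 flagged and 20 unflagged visits.* If the reviewer calls r visits duplications, pe = [20r + 20(40 − r)]/40² = 800/1600 = 0.5 whatever r is. Then kappa = (1 − D/40 − 0.5)/0.5 = 1 − D/20.

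| D | kappa | printed rule (> 0.80) | reversed rule (< 0.80) |
|---|---|---|---|
| 0 | 1.00 | meet | no meeting |
| 1 | 0.95 | meet | no meeting |
| 3 | 0.85 | meet | no meeting |
| 4 | 0.80 | no meeting | no meeting |
| 5 | 0.75 | no meeting | meet |
| 14 | 0.30 | no meeting | meet |

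*Assume 10 and 10.* By the same algebra kappa = 1 − D/10. The printed rule fires at D = 0 or 1 and the reversed rule at D = 3 or more; D = 2 gives exactly 0.80.

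*Assume 10 flagged and 30 unflagged.* Chance agreement now depends on which visits disagree.

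- D = 3, all among flagged visits: po = 37/40 = 0.925 and pe = (10×7 + 30×33)/1600 = 0.6625, so kappa = 0.2625/0.3375 = 0.778.
- D = 3, all among unflagged visits: pe = (10×13 + 30×27)/1600 = 0.5875, so kappa = 0.3375/0.4125 = 0.818.
- By the same method, D = 2 gives 0.857 to 0.875 and D = 4 gives 0.692 to 0.765.

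The printed rule fires at D = 0 to 2 and the reversed rule at D = 4 or more, with D = 3 falling on either side. The review size changes the counts, not the reversal.

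**Step 3: could something else explain or correct the sign?** This is the only mention of kappa in the document, and no separate standard for acceptable agreement is given. A text-conversion fault cannot be excluded from the text alone, but nothing points to one: under Hypothesis 3 the inequality signs came through and make sense ("e.g., <10%, 50%, or >=80% agreement").

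**The case against.** The operative condition is verbal. The parenthesis has no verb and can be read as the standard against which agreement is judged, with adequate meaning above 0.80. On that reading the fault is a misplaced target rather than a reversed sign, and at kappa 0.30 the words would still call the meeting. The sentence shows its intent twice, in the word *poor* and in the aim of remedying a discrepancy, so a team would be unlikely to follow the number over the words. What the rule triggers is only a meeting, for one of four outcomes in a pilot of 60 veterans. The illustrative counts are invented, and the plan does not say how kappa is to be formed from two raters and the criteria.

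Much of this stands, and it limits the consequence. The target reading is probably what was meant. But the sentence does not say it, so that reading also requires a correction. It leaves open whether *poor* covers everything not above 0.80 or only some lower, unstated level. The counts are illustrations only; the contradiction rests on Step 1, which does not use them.

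**Conclusion.** The concern holds. The only numerical threshold for judging the duplication metric contradicts the condition it is attached to. The contradiction itself rests on no assumption; only the disagreement counts depend on assumed review sizes.

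The practical effect is small. It is confined to the validation step for Hypothesis 4, a sensible team would probably follow the word *poor*, and no sample size, alpha level or planned test changes. It should nevertheless be fixed, because it is a pre-specified decision rule that governs whether an outcome measure is remedied before the arms are compared.

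**What to change.** Under Hypothesis 4, change the parenthesis to Kappa < 0.80, or reword the clause to say that kappa of at least 0.80 is the target and the investigative team meets when it is not reached. The second form is clearer, because it also settles what happens at exactly 0.80. The cost is one character or one clause, with no change to data collection, sample size or the Chi-square test.

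Two optional clarifications could be made in the same edit, though the correction does not depend on them: how many unflagged visits will be sampled for review, and that any change to the metric will be settled before results by arm are seen.

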- 1) To conduct a pilot randomized controlled trial comparing usual care to an intervention which aims to improve care coordination for dual use rural veterans by educating them about the use of information technology to share health information and informing their providers about the extent and nature of care from other health care systems.
- 2) To determine the impact of this intervention on patient perceptions of integrated care coordination, provider perception of relational coordination, and the impact of health information sharing as indicated by concordance of medication lists, and lower levels medical duplication when compared with usual care.
- 3) To integrate the results from prior background research and ongoing interventional studies conducted at ICVAHCS into a White Paper that makes recommendations for best practices to improve care in rural settings for veterans who are dual users.
- 4) Exploratory Aim: To explore the acceptability and feasibility of Co-Management Care Coordination Agreements between VA and non-VA providers.

Overview of Pilot Intervention:

The basic structure of the pilot and its evaluation is very similar to that of [name] HSR&D study and her multi-site ORH study. Dual use veterans will be identified through mailed recruitment and screening, they will be trained to use My HealtheVet to improve CC, and their next provider visits will be evaluated for impact of added information, satisfaction, and evidence of medical duplication. Evaluation will be conducted through brief post-visit surveys and patient and provider interviews. [name] experience in her current studies demonstrates the feasibility of these methods including provider completion of the brief evaluation forms.

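### Hypothesis 4 analyses medical duplication only as any versus none, so it cannot compare the number of duplications per patient or give the later trial its mean and dispersion

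*Combined protocol and SAP*

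**What the plan says.** Aim 2 (Specific Aims) expects "lower levels medical duplication when compared with usual care". Under Hypothesis 4 the two components are defined as follows.

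- Therapeutic: "Therapeutic duplication will be defined as concurrent use of more than one medication from the same therapeutic class, based on modified VA classes".
- Laboratory: "we will identify all orders for labs occurring within the 6 months prior to the non-VA provider visit". For sensitivity, "we will compare different intervals, e.g., 14 days, 30 days, 60 days".

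The outcome is then reduced to yes or no, and this is stated twice. The first statement is "Each patient will be assigned a dichotomous indicator for whether they received therapeutic duplication and/or laboratory duplication during their non-VA provider visit". The second, after the validation step, is "Each patient will be assigned a dichotomous indicator for whether they received either therapeutic or laboratory duplication during their non-VA provider visit". The analysis follows: "Differences in the occurrence of medical duplication between usual care and intervention groups will be examined using the Chi-square test". No count, rate or model is named as an alternative.

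For validation, "all instances of identified duplication plus a random sample of visits where no apparent duplication occurred will be reviewed". The section Outcome Assessments and Quantitative Analysis gives the pilot's purpose as estimating effect size and variability for a later power calculation.

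**The concern.** The aim is about how much duplication there is; the endpoint records only whether there was any. Suppose usual-care patients typically carry four duplicated classes or tests and comparable intervention patients carry one. All score yes, and the arms look alike. The indicator registers a lower number only to the extent that more patients reach zero.

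The planning output is limited in the same way. Two proportions support a later trial with another yes/no endpoint. They give no mean or dispersion of the number of duplications, so the pilot could not tell the later trial whether a count would serve it better.

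The plan is more flexible with a similar variable. Under Hypothesis 3 it looks at the distribution of medication concordance before choosing between categories and a continuous analysis. Hypothesis 4 dichotomises without condition.

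**Working it through.** **Inputs.** The Sample section gives 60 veterans. Blocked randomisation with equal distribution between arms is read as 1:1, so 30 per arm. The documents state no alpha, power, effect size, dropout, duplication prevalence or mean count, so there is no plan figure to reproduce. Assumed here: two-sided 5%, no dropout, the mean count halved by the intervention, and a usual-care mean μ ranged from 0.36 to 3. Counts are Poisson (k = 0) or negative binomial with variance μ + kμ², k = 0.5 or 1.

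**Step 1: information kept by the indicator.** Let p0 be the probability of no duplication: exp(−μ) for Poisson, (1 + kμ)^(−1/k) otherwise. The Fisher information on the log mean in the indicator, relative to the count, is

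R = μ·p0 / [(1 + kμ)(1 − p0)],

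which for Poisson is μ/(exp(μ) − 1). At μ = 2 this is 2/(7.389 − 1) = 0.313, so 31% is kept. For k = 1 it simplifies to 1/(1 + μ), which equals p0.

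R falls to one half at:

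- Poisson: μ = 1.26, 71.5% with any duplication
- k = 0.5: μ = 1.12, 59%
- k = 1: μ = 1, 50%

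**Step 2: power with 30 per arm.** There were 3,000 simulated trials per setting, with an uncorrected chi-square on any/none and a Wilcoxon rank sum on the count. The Monte Carlo standard error is at most √(0.25/3000) = 0.9 points.

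| k | Mean, usual care → intervention | With any duplication | R | Chi-square | Wilcoxon |
|---|---|---|---|---|---|
| 0 | 0.36 → 0.18 | 30% → 16% | 83% | 23.6% | 23.9% |
| 0 | 0.7 → 0.35 | 50% → 30% | 69% | 39.0% | 45.2% |
| 0 | 1.25 → 0.625 | 71% → 46% | 50% | 49.6% | 67.4% |
| 0 | 2 → 1 | 86% → 63% | 31% | 55.9% | 85.2% |
| 0 | 3 → 1.5 | 95% → 78% | 16% | 52.9% | 95.9% |
| 0.5 | 0.36 → 0.18 | 28% → 16% | 78% | 20.3% | 21.4% |
| 0.5 | 2 → 1 | 75% → 56% | 33% | 34.7% | 59.8% |
| 0.5 | 3 → 1.5 | 84% → 67% | 23% | 33.0% | 68.5% |
| 1 | 0.36 → 0.18 | 26% → 15% | 74% | 17.6% | 18.7% |
| 1 | 2 → 1 | 67% → 50% | 33% | 27.2% | 42.1% |
| 1 | 3 → 1.5 | 75% → 60% | 25% | 23.4% | 47.0% |

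In a separate run of 4,000 trials per setting with no difference between arms (k = 0.5, means 1.5 and 3), both tests rejected in 4.6% to 5.1%.

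**Step 3: summed or separate counts.** The indicator pools two components, so a fair comparator must pool them too. With two independent components, each mean halved, simulated power was:

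| Mean per component | Composite any/none | One component's count | Summed count |
|---|---|---|---|
| Poisson 0.5 | 46% | 31% | 56% |
| Poisson 1 | 57% | 56% | 85% |
| Negative binomial, k = 0.5, mean 1 | 42% | 42% | 70% |

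At a mean of 0.15 per component, the composite and the summed count were about equal. The Poisson summed entries are single-count results at means 1 and 2, since two independent Poisson counts sum to a Poisson count.

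**Step 4: where the composite prevalence might lie.** If the components are independent, the share with either is 1 − (1 − pT)(1 − pL). Two components at 30% give 1 − 0.7² = 51%; two at 50% give 1 − 0.5² = 75%. Pooling can therefore carry moderate component rates into the range where Step 1 shows a large loss, but the documents do not say what the rates are.

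**The case against.** **The size of the loss is not established.** No duplication rate is given, eligibility requires one listed condition and no minimum number of drugs, and the shorter laboratory windows would lower that component. This stands. A reader might infer that the indicator saturates in multi-drug patients and so discards most of the information; the documents support neither the multi-drug description nor a rate near the ceiling.

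**The indicator can still respond.** In every row of the Step 2 table it falls when the mean is halved, and its power is well above 5%. This stands against any inference that the pilot would necessarily report no effect.

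**No patient's change is scored.** Table 2 has no baseline duplication measure and Hypothesis 4 compares arms after the visit. A reader might picture a patient improving from four duplications to one and being recorded as unchanged; the design has no such within-patient comparison. The loss is in the comparison between arms.

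**Separate component counts are no improvement at low or moderate means.** Step 3 confirms this, and testing two counts adds multiplicity. It rules out replacing the indicator by two separate tests, but it does not apply to the summed count.

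**Validation rests on presence or absence.** The reviewers judge whether duplication is present, and agreement is measured by kappa. For constructs that the plan itself calls hard to operationalise, a simple indicator is defensible. This stands as a cost: a count needs its own rule and check.

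**This is an estimation pilot, and two proportions are an effect size.** Low power alone is indeed no error here, and Aim 2 could be read as a lower group rate. But the proportions serve only a later binary endpoint and leave the count unsummarised, although the instances behind it are identified.

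**Conclusion.** The point holds in a conditional form. At any prevalence, the planned analysis cannot compare the number of duplications per patient and yields no mean or dispersion of that number for the later trial. The statistical loss depends on an unknown rate. It is slight if duplication is rare: at a mean of 0.36 the indicator keeps 74% to 83% of the information and the two tests have nearly the same power. It exceeds half only when any-duplication prevalence is above about 72% (Poisson), 59% (k = 0.5) or 50% (k = 1). Where means are higher the power gap is wide, for example 35% against 60% at a mean of 2 with k = 0.5. The simulated power of the summed count was at least about equal to the indicator's in every setting.

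These figures rest on the assumed means, a halving of the mean, 30 per arm with no loss, and, in Step 3, independent components. They do not show that the indicator will be near its ceiling in this population.

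**What to change.** Make the main Hypothesis 4 comparison the total number of duplications per patient: duplicated therapeutic classes plus duplicated laboratory tests, each class or test counted once. Compare arms with a Wilcoxon rank sum test, or with a negative binomial or robust Poisson model giving a rate ratio and 95% CI; choose one in advance. Report mean and SD by arm for the total and for each component, without treating the components as separate main tests. Keep the any/none indicator with its chi-square test as a secondary summary.

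No new data collection is needed. The costs are a written counting rule, a blinded review that checks agreement at instance level as well as on presence, and an outcome slightly harder to explain than a percentage. The counting rule should also name the visit it applies to, because Table 2 lists medical duplication after both the VA and the non-VA visit while Hypothesis 4 uses only the latter.
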